Week 2 - 54	1.2 or 1.8 mg	1.2 or 1.8 mg

Packaging and Labeling of Study Medications: Packaging and labeling of the trial products will be handled by the manufacturer (Novo Nordisk A/S). Liraglutide and its vehicle will be administered via pens supplied by the manufacturer (Novo Nordisk A/S).

Storage and Drug Accountability of Study Medications: The research pharmacist will inventory and acknowledge receipt of all shipments of the study drug. The study drug will be kept in a locked area with restricted access. The study drug will be stored in a refrigerator between 36°F to 46°F (2°C to 8°C), in a secure location. After initial use, the pen can be stored for 30 days at controlled room temperature (59°F to 86°F; 15°C to 30°C) or in a refrigerator (36°F to 46°F; 2°C to 8°C), with the pen cap on when not in use. The pen should be always protected from excessive heat and sunlight.

The PI, pharmacist, or designee is responsible for maintaining accurate records of the receipt, dispensing, proper storage, and return of all investigational materials. Cedars Sinai Investigational Drug Pharmacy will be the designee to control on-site storage conditions of the drug prior to dispense. Temperature logs are maintained and archived indefinitely. At study closure, printed logs are provided in the pharmacy binder for the duration of study drug storage. The PI, pharmacist, or designee may dispense study drug only to subjects enrolled in the study. Under no circumstance will the PI, pharmacist, or designee allow study drug to be used other than as directed by the protocol. When a shipment is received, the research Pharmacist or designee must verify the quantities received and return the acknowledgement to the Drug Manufacturer or designee. The study drug accountability record includes the identification of the subject to whom the drug is dispensed, the lot number on the pen, the date of dispensing, and any returned or unused drug. An account must be given of any discrepancies. These records must be readily available for inspection by any relevant Health Authority at any time. The Investigational Drug Pharmacy will destroy unused drug following institutional drug destruction policy and will maintain a record of destruction of the drug incinerated off-site via the hospital's contracted pharmaceutical waste vendor, Stericycle.

Randomization and Blinding: The study drug will be administered according to the clinical study

protocol only to subjects who have signed the informed consent form (ICF).

At the end of the Baseline visit (see Study schedule), each subject meeting entry criteria will be randomly assigned to one of the two treatment groups in a 2:1 ratio (liraglutide or placebo).

A pre-determined randomization list generated by our biostatistics team will be given to and maintained by pharmacy staff. Once assigned, codes will not be reused for any other subjects in the study. In data collection records, subjects will be designated only by these de-identified codes. The randomization schedule so generated will be maintained by the investigational pharmacist, who will remain the only unblinded study staff member.

The liraglutide and matching placebo injection pens will be identical and indistinguishable to the Investigators, the subjects or others assisting in treatment administration. In accordance with the double-blind design, all these individuals will remain blinded to study treatment and will not have access to the randomization (treatment) codes except under the circumstances described below.

Breaking of Blinded Codes: The blinding code may be broken only in exceptional circumstances when knowledge of the study drug is essential for treating the subject, such as in case of an adverse event. Code breaking can be performed by the PI or authorized designee at any time by opening a sealed envelope containing unblinding information provided by the pharmacy staff. The Investigator or the designee who breaks the blind must record the date and the reasons for doing so in the source documentation and in the subject's medical records

CONCOMITANT ILLNESSES AND MEDICATIONS: See Inclusion and Exclusion Criteria

ADVERSE EVENTS:

Collection, Recording, and Reporting of Adverse Events (AEs): The collection of non-serious AE data and serious adverse event (SAE) information commences following the subject's written consent to participate in the study. An AE is any untoward medical occurrence in a clinical investigation subject administered an investigational product and which does not necessarily have to have a causal relationship with this treatment. An AE can therefore be any unfavorable and unintended sign (including an abnormal laboratory finding, for example), symptom, or disease temporally associated with the use of a medicinal product, whether or not considered related to the medicinal product (study drug). An Adverse Reaction (AR) is an AE for which a causal relationship to the trial product is at least possible, i.e. a causal relationship is conceivable and cannot be dismissed.

The description of each AE will identify the subject, date of onset, the date of resolution, the severity of the event, the action taken regarding study drug, the outcome of the event, and the relationship of the event to study drug. AE information will be entered in the CRF within 7 days of the information becoming available in order to ensure timely reporting to the Sponsor.

Severity of reported AEs will be evaluated using the following guidelines:

- Mild: The subject is aware of the AE but it is easily tolerated.
- Moderate: The AE causes the subject discomfort and interrupts the subject's activities of daily life.

- Severe: The AE is debilitating or results in the inability of the subject to perform the activities of daily life.

The Investigator will use the following definitions to evaluate the relationship of each AE to the study drug:

Definitely: An AE that follows a reasonable temporal sequence from administration of the study drug (including the course after withdrawal of the study drug) and that satisfies any of the following:

- reappearance of a similar reaction upon re-administration (positive rechallenge);
- toxic level of the study drug as evidenced by measurement of study drug concentrations in blood or other bodily fluid.

Probably Related: An AE that follows a reasonable temporal sequence from administration of the study drug (including the course after withdrawal of the study drug) and for which involvement of factors other than the study drugs, such as underlying diseases, complications, concomitant drugs, and concurrent treatments, can reasonably be excluded. This may also include positive dechallenge, in which the event abates upon discontinuation of the study drug.

Possibly Related: An AE that follows a reasonable temporal sequence from administration of the study drug (including the course after withdrawal of the study drug) and for which possible involvement of the study drug can be suggested (for example, previous similar reports or pharmacologic actions of the study drug) although factors other than the study drug, such as underlying diseases, complications, concomitant drugs, and concurrent treatments may also be responsible.

Unlikely: An AE that, while not necessarily unrelated to the study drug, does not appear to follow a reasonable temporal sequence from administration of the study drug or that appears to be reasonably explained by other factors, such as underlying diseases, complications, concomitant drugs, and concurrent treatments.

Not related: An AE that does not follow a reasonable temporal sequence from administration of the drug or that can reasonably be explained by other factors, such as underlying diseases, complications, concomitant drugs, and concurrent treatments.

The liraglutide US Prescribing Information document will be used for evaluations of expectedness, as agreed with the drug manufacturer.

An **SAE** is an experience that, at any dose, results in any of the following:

- Death;
- A life-threatening event in which the patient is at risk of death at the time of the event. Note: it does not refer to an event that hypothetically might have caused death if it was more severe.
- In-patient hospitalization or prolongation of an existing hospitalization;
- Persistent or significant disability/incapacity;
- Congenital anomaly or birth defect in the offspring of the subject (whether the subject is male or female);
- Need of medical or surgical intervention to preclude permanent impairment of a body function or permanent damage to a body structure;

- An important medical event: Those events that may not be immediately life-threatening or result in death or hospitalization but based upon appropriate medical and scientific judgment may jeopardize the subject or may require intervention to prevent one of the serious outcomes listed above.
- Suspicion of transmission of infectious agents must always be considered an SAE.

A Serious adverse reaction (SAR) is an adverse event that fulfils both the criteria for a Serious Adverse Event and the criteria for an Adverse Reaction.

A Suspected Unexpected Serious Adverse Reaction (SUSAR) is a SAE that is unexpected and regarded as possibly or probably related to the trial/study product by the investigator.

SAEs require expeditious handling to comply with regulatory requirements. Any SAE, SAR or SUSAR occurring in a clinical study subject will be reported to the Institutional Review Board (IRB) within 10 days of the Investigator having knowledge of the SAE. In addition, the investigator will copy Novo Nordisk A/S (NN) when expediting SARs or SUSARs to health authorities and will report all SARs related to NN Product to the local NN affiliate safety department. The submission to NN will be within day 15 from the investigator's first knowledge about a valid case. The Investigator or other qualified individual at the investigative site will complete an SAE form including study name, name of the reporter, subject identification (e.g. subject number, initials, gender, age), event (preferably diagnosis), study drug, most recent date of administration, the Investigator's causality assessment to study drug (as outlined above) and outcome.

Follow-up of Adverse Events: If a subject experiences an SAE or AE, the subject will receive appropriate treatment and supportive care, as necessary, and the PI will continue to follow-up until there is a return to the subject's baseline condition, or until a clinically satisfactory resolution is achieved.

Pregnancy Beginning During Course of Trial: Female study subjects will be advised by the Investigator to inform him immediately if she suspects she may be pregnant up to 30 days after the last dose of study drug.

Male study subjects will be advised by the Investigator to inform him immediately if he suspects his partner became pregnant up to 30 days after the last dose of study drug.

When a study subject reports a possible pregnancy to the PI after the start of drug administration, study drug should be stopped immediately and a pregnancy test should be arranged for the subject (or partner) by the PI within 7 days of the pregnancy being reported. In the case of pregnancy, the PI must immediately notify the Drug manufacturer of this event and report the pregnancy in the source documentation. This includes a study subject as well as the partner of a study subject who becomes pregnant while the subject was receiving study drug. Every attempt will be made to follow the pregnancy to conclusion to obtain information regarding the outcome. All pregnancies in trial subjects exposed to the study drug will be reported to the drug manufacturer (Novo Nordisk A/S).

Precautions/Over-dosage: Based on previous studies with liraglutide in patients with type-2 diabetes,⁷⁶ the following percentages of cases are expected to experience mild-to-moderate nausea (5-40%), diarrhea (17%), constipation (10%), and/or headache (9%). Subjects will be asked to report these or any other adverse effects when they arise and during each of the scheduled visits (see Study Schedule).

Overdoses have been reported in clinical trials and post-marketing use of liraglutide, with resulting effects including severe nausea and vomiting. In the event of over-dosage, appropriate supportive treatment will be initiated according to the subject's clinical signs and symptoms.

LIABILITY AND SUBJECT INSURANCE: A research-related injury or illness is a direct result of the study drug or a procedure performed only as a part of the study and is not part of standard clinical medical treatment. Cedars-Sinai has no plans to pay for costs associated with the treatment of research-related injury or illness. If a study subject will need treatment for a research-related injury or illness, Cedars-Sinai Health System will make every effort to seek reimbursement from his/her health plan. The subject will be responsible for any deductibles and co-payments required under his/her health plan and for any claims ultimately denied by the health plan. Financial assistance may be available under Cedars-Sinai's Charity Care Policy and Procedure. Losses such as lost wages will not be paid.

PREMATURE TERMINATION OF STUDY: In case the study is terminated early due to the discovery of an unexpected, significant, or unacceptable risk/safety concern, regardless of how far along the subject has reached in their study follow-up, subjects will be asked to return all unutilized pens to the PI. The study site will then return investigational drug to the drug manufacturer (See also Study Drug Accountability).

PUBLICATION PLANS: The intention of the study will be to publish the results of the complete study at conclusion. All information obtained during the conduct of this study will be regarded as confidential but no written permission from the study funding sources is required prior to disclosing any information relative to this study. A formal publication of data collected as a result of the study will be considered a joint publication by all investigators and appropriate personnel. Authorship will be determined by mutual agreement. Submission to the funding source(s) for review and comment will be intended solely to ensure concurrence regarding data, evaluations, and conclusions, and to provide an opportunity to share with them any new or unpublished information of which they may be unaware.

Schedule of events

Procedures	Screening	Baseline	Week 1	Week 2	Week 3	Week 6	Week 14	Week 28	Week 40	Week 54	Week 58	Week 80	Week 108
Day	Within 30 days of baseline	1	8 + 3	(7+3 days from Week 1)	(7+3 days from Week 2)	42 ± 7	98 ± 7	196 ± 7	280 ± 7	378 ± 7	406 ± 7	560 ± 7	756 ± 7
Sign Consent	x												
Demographics	x												
Medical History	x												
Pregnancy Test	x												
Physical and Neuro Exam	x												
EKG	x		x	x		x	x	x	x	x		x	x
Vitals	x	x	x	x		x	x	x	x	x		x	x
Blood and Urine samples¹	x		x	x		x	x	x	x	x		x	x
Blood for Biomarker Analysis	x							x		x		x	x
Review of eligibility		x											
MDS-UPDRS OFF²		x						x		x		x	x
MDS-UPDRS ON		x						x		x		x	x
BDI-II	x												
NMSS		x						x		x		x	x
MDRS-2	x							x		x		x	x
Neuropsych tests		x						x		x		x	x
Treatment Randomization and First Dose		X (0.6) Placebo	X (1.2) Placebo	X (1.8) Placebo									
Drug Administration Training		x	x	x									
Dispense Study Drug		x	x	x		x	x	x	x				

Review Study Drug Compliance			X	X		X	X	X	X	X			
AE Assessment	X	X	X	X	X	X	X	X	X	X	X	X	X
Assessment of Concomitant Medications		X	X	X	X	X	X	X	X	X	X	X	X
Final dosage determination³					X								

1) Lab tests – schedule across study:

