Study Type: This is a phase II, randomized, double-blinded, placebo-controlled clinical trial.

STUDY POPULATION:

Cases: Fifty-seven patients with a diagnosis of idiopathic PD will be recruited and randomized to receive once daily self-administered injections of liraglutide (1.2 or 1.8 mg, as tolerated) or placebo at the same dose range in a 2:1 study design.

Inclusion Criteria:

- Diagnosis of idiopathic PD according to the United Kingdom Parkinson's Disease Society Brain Bank (UKPDSBB) criteria^a for at least 2 years, and/or a DaT-confirmed diagnosis of PD
- Responsive to levodopa or dopaminergic treatment
- Male or female between 25 and 85 years of age at time of enrollment
 - Women of child-bearing potential (WOCBP) must agree to use a reliable method of contraception (e.g., oral contraceptive or long-term injectable or implantable hormonal contraceptive, double barrier methods (such as condom plus diaphragm, condom plus spermicide foam, condom plus sponge), or intra-uterine devices) throughout the duration of the trial period and must have a negative serum pregnancy test at screening
 - Male patients with female partners who have child bearing potential must agree to use adequate contraception throughout the duration of the trial period

- Capacity to give informed consent
- Ability to self-administer, or to arrange a care partner to administer trial drug, to comply with trial protocol, and to attend necessary clinic visits off medication

a: Note: the study team will not consider the UKPDSBB criterion “more than one affected relative” as exclusionary. According to the scientific community, family history is not regarded as exclusionary and this specific criterion is no longer used (reference).

Exclusion Criteria:

- Diagnosis or suspicion of other causes for Parkinsonism, including drug- or toxin-induced parkinsonism and other neurodegenerative conditions, including multiple system atrophy, progressive supranuclear palsy, Huntington's disease, Wilson's disease, or Alzheimer's disease
- Active treatment with anticholinergic medications (e.g., trixyphenidil or tricyclic antidepressants)
- Known abnormality on CT or MRI brain imaging considered to cause symptoms or signs of neurological dysfunction, or considered likely to compromise compliance with trial protocol
- Concurrent dementia defined by a score lower than 120 on the MDRS-2 and/or inability to complete scale per neuropsychologist’s discretion

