- Concurrent severe depression defined by a score greater than 29 on the Beck Depression Inventory (BDI-II)
- Prior intracerebral surgical intervention for PD, including deep brain stimulation, lesional surgery, growth factor administration, gene therapy, or cell transplant
- Already actively participating in a trial of a device, drug, or surgical treatment for PD, or trial participation within 30 days prior to the baseline visit
- Diagnosis of diabetes mellitus of any type, established historically or by:
 - Fasting plasma glucose levels equal or above 126 mg/dl
 - Hemoglobin A1c equal or above 6.5%
- Active treatment with oral antidiabetic medications
- History of severe cardiac disease (e.g., angina, myocardial infarction, or cardiac surgery) in the preceding year
- Significant systemic illness likely to result in deterioration of the patient's condition or, in the Investigator’s opinion, affect the patient's safety during the study, including in particular:
 - 1) History of pancreatitis
 - 2) Personal or family history of medullary thyroid carcinoma
 - 3) History of multiple endocrine neoplasia syndrome type 2
 - 4) History of alcoholism
 - 5) Severe gastrointestinal disease, including gastroparesis
 - 6) Treatment with immunosuppressive medications (e.g., systemic corticosteroids) within the last 90 days or chemotherapeutic agents for malignancy within the last 2 years
 - 7) Severe renal insufficiency (CrCl <30)
 - 8) Moderate or severe hepatic impairment
 - 9) Severe hypertriglyceridemia (triglycerides >500 mg/dl)
 - 10) Body mass index <18.5
- Females who are pregnant or breast feeding
- Prior serious hypersensitivity reaction to Victoza or any of the product components

Withdrawal Criteria: In the absence of a medical contraindication or significant protocol violation,

every effort will be made by the Principal Investigator (PI) to keep accepted subjects in the study. However, should the subject decide to discontinue treatment, all efforts will be made to complete and report the observations as thoroughly as possible, including a complete final evaluation at the time of the subject's withdrawal with an explanation of why the subject is withdrawing from the study. All subjects who prematurely withdraw from the study will receive a follow-up telephone call one month after discontinuation. Study treatment will be stopped if any of the following events occur:

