- The subject has any clinical AE, laboratory abnormality, intercurrent illness, or other medical condition that indicates to the PI that continued participation is not in the best interest of the subject or if it requires the subject to stop taking levodopa or other medications essential to the treatment of Parkinson's disease. Subjects experiencing AEs that are present at the end of their participation in the study should receive follow-up, as appropriate. If possible, the outcome of any AE resulting in withdrawal from the study or that was present at the end of the study will be followed until resolution or return to baseline condition, particularly if the AE was considered by the PI to be related to the study drug;
- The subject requires a concomitant medication that is prohibited in the study;
- The subject wishes to withdraw consent from the study in the absence of a medical need to withdraw, as determined by the Investigator;
- The PI concludes that it is in the best interest of the subject to discontinue study treatment;
- The subject is noncompliant; or
- If pregnancy is suspected while the subject is receiving study treatment, the study medication must immediately be withheld until the result of pregnancy testing is known. If pregnancy is confirmed, the study medication will be permanently discontinued and the subject withdrawn from the study. Reasonable attempts will be made to follow the pregnancy to conclusion in order to obtain information regarding the outcome.

The PI must complete all applicable final visit procedures (e.g., safety laboratory parameters, ECG, physical examination, vital signs [including orthostatic BP and HR]) and study documentation for subjects who withdraw from the study treatment and specify the reason for their withdrawal. Once subjects withdraw from the study, they will revert to the care of their usual physician for treatment/management of their disease as appropriate.

Subject Replacement: A subject who withdraws from the study may not reenter the study.

Rationale for Study Population: (see Background and Significance)

Visit Procedures: (see Study Schedule)

Assessments for Efficacy: The efficacy of liraglutide will be assessed by measures of the drug's effects versus placebo on PD motor and non-motor symptoms quantified on the following scales after study medication titration in active and placebo groups:

- MDS-UPDRS part I, II, III and IV changes from ON medication baseline at 28 and 54 weeks

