DATA/SAMPLE HANDLING AND RECORD KEEPING: The Investigator will delegate responsibility for data entry and quality to a named individual who will be part of the trial team, in accordance with the Data Protection Act of 1998. The Investigator will be responsible for data analysis done independently of data entry. The Cedars-Sinai Core Statistical team will be on hand with additional advice.

The plasma samples for EV analysis will be stored in the Advanced Health Sciences Pavillion building in a -80°C freezer.

ETHICS: The trial will comply with ICH GCP and applicable regulatory requirements and proceed in

accordance with the Declaration of Helsinki. Prior to the start of the study, the Investigator will apply for approval of the study from the Cedars-Sinai IRB. All documents required by the IRB and the regulatory authority will be submitted. Any notification/submission must be dated and contain sufficient information to identify the relevant protocol. The study will only commence after receipt of written approval from the Cedars-Sinai IRB. The Investigator designee is responsible for maintaining the approval documents in the Investigator study files. The Investigator will report promptly to the IRB any new information that may adversely affect the safety of the patients or the conduct of the trial. At the end of the study, the Investigator is obligated to inform the IRB in writing that the study has ended and no further activities regarding this protocol will be conducted at the site

STUDY SCHEDULE: The trial will be conducted in the Neurology Department of the Cedars-Sinai Medical Center in Los Angeles, CA, according to the following schedule of events. Enrollment is expected to start (FPFV) on July 1st, 2016 and conclude (LPLV) on June 30th 2018.

Screening and information visit

The informed consent will take place after the study candidate has received extensive oral and written information about the study, including the risks associated with the study procedures and study-drug, prior to any study-related activity, including screening procedures. After consenting, detailed information will be collected on all study candidates, including demographics and relevant medical history, MDRS-2 screening, BDI-II screening, physical and neurological exams, routine vitals (height, weight, blood pressure in clino- and orthostatic positions), an EKG, and blood and urine tests. For women of child-bearing age, a serum pregnancy test will also be performed.

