Baseline evaluation visit

After confirmation of eligibility criteria, subjects will subsequently be randomized to one of the two treatment arms. They will then undergo MDS-UPDRS OFF and ON testing and Neuropsychological testing (ON). The practically defined OFF condition will be considered an overnight withdrawal of dopaminergic medications for 12 hours while ON evaluation will be performed 1 hour (\pm 15 minutes) after the administration of the usual morning dose of dopaminergic medications. The first daily dose of 0.6 mg and/or placebo, including injection instructions, will be administered at the end of the baseline visit. The baseline visit is to be conducted within 30 days of screening.

Commence treatment: 2-week titration

The following two visits will be dedicated to medication titration, up to 1.2mg (Week 1) and 1.8 mg (Week 2), as tolerated. At every visit, study drug compliance will be reviewed. Adverse events will be assessed and concomitant medications, routine vitals, and ECG, and blood and urine tests will be collected. A phone interview will be conducted following titration to determine which dosage (1.2 mg or 1.8 mg) the patient will remain on for the duration of the study.

Follow-up visit 1 and 2

4 and 12 weeks after titration is completed, a follow-up visit will establish whether the subjects are tolerating study medications, including an assessment of adverse events, concomitant medications, routine vitals, an ECG, and blood and urine tests.

Follow-up visit 3 (6 month)

26 weeks after completing titration, subjects will undergo repeat MDS-UPDRS OFF and ON testing and

Neuropsychological testing (ON) in addition to an assessment of adverse events, concomitant medications, routine vitals, an ECG, and blood and urine tests.

Follow-up visit 4 (9 months)

36 weeks after titration is completed, a follow-up visit will establish whether the subjects are tolerating study medications, including an assessment of adverse events, concomitant medications, routine vitals, and ECG, and blood and urine tests.

End visit

52 weeks after completing titration, subjects in both treatment arms will undergo an exit visit including MDS-UPDRS OFF and ON testing and neuropsychological testing (ON) in addition to an assessment of adverse events, concomitant medications, routine vitals, an ECG, and blood and urine tests. At this stage, study treatment will be discontinued.

Post-study visit

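### The only scheduled pregnancy test is at screening, up to 30 days before the first dose, with none at Baseline or during the 54 weeks on drug

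*Combined protocol and SAP*

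**What the plan says.** The Inclusion Criteria set two conditions: "Women of child-bearing potential (WOCBP) must agree to use a reliable method of contraception" for the duration of the trial, and each such woman "must have a negative serum pregnancy test at screening". The Exclusion Criteria bar "Females who are pregnant or breast feeding".

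The narrative for the screening visit agrees: "For women of child-bearing age, a serum pregnancy test will also be performed". In the Schedule of events, the row "Pregnancy Test" is marked at Screening only.

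On timing, the Baseline section states: "The baseline visit is to be conducted within 30 days of screening". Eligibility is reviewed at that visit, and the first 0.6 mg dose is given at its end.

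Other pregnancy testing is triggered by events. The Withdrawal Criteria require the drug to be withheld pending a test "If pregnancy is suspected while the subject is receiving study treatment". The section on pregnancy during the trial says: "Female study subjects will be advised by the Investigator to inform him immediately if she suspects she may be pregnant". Once a possible pregnancy is reported, the drug stops and a test is arranged within 7 days. A note under the laboratory schedule also allows tests to be repeated if the team is concerned about accuracy or safety.

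**The concern.** Pregnancy is an exclusion that has to hold when dosing starts, but the plan verifies it only at screening. A conception shortly before the screening test may be too early to show, and one between screening and Baseline cannot show. Either woman could be randomised and dosed with every scheduled step followed.

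During treatment, detection depends on someone suspecting a pregnancy. That is a weak trigger in this trial. The Precautions section expects nausea in 5-40% of cases, constipation in 10% and headache in 9%, so early symptoms of pregnancy could easily be put down to study drug. Exposure would continue until the pregnancy was suspected, when a scheduled test might have ended it sooner.

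The protocol treats exposure in pregnancy as serious: drug withheld at once on suspicion, permanent discontinuation on confirmation, notification of the manufacturer and follow-up of the pregnancy. Scheduled detection would match that strict response.

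**Working it through.** The plan gives no figure of its own to reproduce. The check sets the relevant sections side by side and does the day arithmetic.

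**Where a pregnancy test is scheduled**

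| Source | Pregnancy test |
|---|---|
| Inclusion Criteria | Serum, at screening |
| Screening visit narrative | Serum, at screening |
| Schedule of events, 13 visit columns | Marked in the first (Screening) only |
| Baseline narrative and column | None; no blood or urine sample is scheduled |
| Laboratory footnote, Weeks 1, 2, 6, 14, 40 | Not listed; urinalysis is |
| Laboratory footnote, Weeks 28, 54, 80, 108 | Not listed; urinalysis is |

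The table row, the narrative and the footnote agree, so the gap is not an artefact of how the table was extracted.

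**Inputs from the Schedule of events:** Baseline = Day 1; Week 6 = Day 42; Week 14 = Day 98; Week 28 = Day 196; Week 40 = Day 280; Week 54 = Day 378. Each of the visits from Week 6 on has a window of ±7 days. Screening is at most 30 days before Baseline.

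**Intervals as planned**

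- Test to first dose: up to 30 days.
- First dose to end of treatment: 378 − 1 = 377 days, or 377 + 7 = 384 with the window.
- Test to end of treatment: 30 + 377 = 407 days, or 407 + 7 = 414 with the window.

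**Intervals with tests at Baseline and Weeks 6, 14, 28 and 40**

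- Test to first dose: same day.
- Baseline to Week 6: 42 − 1 = 41 days.
- Weeks 6 to 14: 98 − 42 = 56 days.
- Weeks 14 to 28: 196 − 98 = 98 days.
- Weeks 28 to 40: 280 − 196 = 84 days.
- Week 40 to end of treatment: 378 − 280 = 98 days.
- Longest: 98 days, or 98 + 14 = 112 if one visit is 7 days early and the next 7 days late.

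**Feasibility.** After Baseline, the visits with both urine collection and drug dispensing are Weeks 1, 2, 6, 14, 28 and 40. Each on-treatment test proposed here therefore uses urine already collected and can be read before drug is handed out.

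**The case against.** The sections are consistent with one another and nowhere promise repeat testing, so the plan breaks no rule of its own. It also has several safeguards: mandatory contraception, the exclusion itself with eligibility reviewed at Baseline, withholding on suspicion, the instruction to report, a test within 7 days of a report, adverse-event assessment at every visit, and the discretion to repeat laboratory tests. The documents give no reproductive-toxicity data from which to derive a testing frequency, so any particular timetable is a judgement. The number of women concerned is probably small: 57 planned patients with Parkinson's disease (at most 63) aged 25 to 85, with no more than 42 exposed to drug.

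Most of this stands as a limit on the size of the problem. The interval figures describe the calendar between scheduled tests, and nothing in the documents converts them into exposure avoided. Even with the added tests, gaps of 98 days remain, so suspicion and reporting would still be an important safeguard.

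It does not remove the gap. Each post-screening safeguard against an undetected pregnancy needs someone to suspect it first, and agreeing to contraception does not show that it worked. The eligibility review at Baseline has no newer result to draw on than the one from screening.

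**Conclusion.** The point holds. One pregnancy test is scheduled, at screening; there is none at Baseline and none from Week 1 to Week 54. The result can be 30 days old at first dose, and up to 407 days (414 with the window) can pass between that test and the end of treatment. These figures assume the maximum screening interval and treatment to the planned Week 54 visit.

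It is a minor, inexpensive improvement to safety monitoring. The clearest part is the stale result at first dose, which a Baseline test closes completely. Testing on treatment shortens the time a pregnancy can go without a scheduled check but does not remove it. The practical effect depends on how many women of child-bearing potential enrol, which the documents do not say and which may be zero.

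**What to change.** For women of child-bearing potential:

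1. Mark the pregnancy-test row at Baseline and require a negative result before randomisation and first dose.
2. Add a urine pregnancy test at on-treatment visits where urine is already collected and drug is dispensed, for example Weeks 6, 14, 28 and 40, read before dispensing. The choice of weeks is open. Week 54 is not needed for this purpose because treatment stops there.
3. Amend the Inclusion Criteria, the Baseline narrative and the laboratory footnote to match.

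The cost per woman of child-bearing potential is one extra urine sample and test at Baseline, where no sample is now taken, and about four inexpensive tests on urine already collected. If no such woman enrols, no tests are needed. If only one change is made, it should be the Baseline test.
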